4.2.2.4 Tipping Point analysis

Tipping point analyses will also be implemented as a supportive analysis for the primary efficacy endpoint. This analysis will be performed only for the subjects randomized to Placebo and BKZ.

The objective of the tipping point analyses is to identify assumptions about the missing data under which the conclusions from the main analysis change (ie: under which there is no longer

evidence of a treatment effect). These tipping point analyses will only be performed if the primary efficacy analysis results in a statistically significant treatment effect ($p < 0.05$).

As a first step, the worst-case scenario will be evaluated. Specifically, all BKZ randomized subjects with a missing ACR50 at Week 16 (or non-missing ACR50 after study treatment discontinuation) will be imputed as non-responders, while all placebo-randomized subjects with a missing ACR50 at Week 16 will be imputed as responders. While there is little justification for such an approach, it makes the most putative assumption possible against a BKZ treatment effect. After applying this imputation approach, a logistic regression model consistent with the one described for the primary analysis will be applied. If the p-value for the OR of BKZ versus placebo is < 0.05 , then no further tipping point analyses are needed.

If this analysis based on the worst-case scenario results in a $p > 0.05$, then additional tipping point analyses will be performed. In practice, it implies different delta adjustments will be made to the assumed responses on the missing data (where missing values include observations after the IE date and any other missing values) in each treatment group independently with various degrees of plausibility with the goal to find for each treatment group the “tipping point” that will significantly reverse the primary result which yielded a $p < 0.05$. These delta adjustments will be done on each component of ACR50 as follows:

- Step 1: The same MCMC method described in [Section 4.2.2.2](#) will be implemented for non-monotone (intermittent) missing pattern values, using the same imputation model. This will be based on 100 imputations.
- Step 2: Based on the datasets obtained in Step 1, a monotone regression model will be applied (using the same imputation model as in Step 1) and as described in [Section 4.2.2.2](#). This will be based on 1 imputation.
- Step 3: Imputed values will be shifted using a delta adjustment independently in each treatment group.

Once defined, the same delta adjustment value will be applied on the imputed values for the Week 16 visit only. The selected scenario will assume that subjects randomized to BKZ and who have missing data have a lower probability of response compared to subjects randomized to placebo with missing data.

- For ACR components for which high scores are associated with a less favorable outcome, it will mean that:
 - A positive shift is applied to the imputed value for subjects randomized to BKZ to increase the imputed value.
 - A negative shift is applied to the imputed value for subjects randomized to placebo to decrease the imputed value.

A set of possible values will be first pre-defined for the delta parameter as below:

- For all ACR component, the value of the initial delta parameter will be equivalent to a specific percentage of the possible range of each component (i.e. 5%). For hs-CRP, the range will be based on the log-transformed values at Week 16. The delta parameters for each endpoint are listed in the table below:

Table 4-3: Tipping point analysis: Delta parameter for each ACR component

ACR component ¹	Range	Delta
SJC	0-66	3.3
TJC	0-68	3.4
HAQ-DI	0-3	0.15
PtAAP, PhGA-PsA, PGA-PsA	0-100	5
hs-CRP ²	Observed range of the log _e transformed values for all BKZ and Placebo subjects (at Week 16)	5% of the observed range

¹The shifted imputed value should not exceed the range for the ACR component.

²The delta adjustment will be applied on the log_e transformed imputed and observed values which will then be exponentiated prior to deriving endpoint.

- Step 4: Standard rounding rules will be applied to the imputed values. If the SAS® PROC MI yields a value outside of the range for the given component, the value will be updated after the imputation has been performed to be within the predefined range.
- Step 5: Repeat Steps 1 to 4 for each ACR component. The composite binary endpoint (ACR50) will then be derived based on the multiply shifted imputed datasets obtained for each component.
- Step 6: Additionally, as the primary endpoint is derived using NRI, subjects randomized to BKZ with missing data (where missing values include observations after the IE date and any other missing values) should be set to non-response, after applying the delta adjustment outlined in Step 3 above. This ensures subjects randomized to BKZ do not have a higher probability of response in the tipping point analyses compared to the primary analysis (i.e. a subjects randomized to BKZ who is non-responder in the primary analysis cannot become a responder in the tipping point analyses).
- Step 7: In the data obtained, for each value of the imputation number, ACR50 will be analyzed using a logistic regression model with factors of treatment group, regions, and bone erosion at Baseline as fixed effects.
- Step 8: The results obtained from the 100 logistic regression analyses in Step 6 will be combined for overall inference using Rubin's rules, and the results obtained for each shift parameter will be presented in a single table.
- Step 9: Step 3 to 8 will be repeated so that, at each iteration, missing values are adjusted with a larger shift than at the previous iteration. Depending on the results obtained, delta parameters with more granularity (eg, 2 times, 3 times the initial delta, etc.) will be investigated. The process will go on until the p-value for the OR between BKZ and placebo is no longer statistically significant (ie ≥ 0.05). The OR, 95% CI, and p-values obtained for each value of delta will be combined in one single table.

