4.2.2.1 Non-responder imputation

For binary endpoints, the non-responder imputation (NRI) analysis, also described above as the composite estimand, will consider the following subjects as “non-responders” for the timepoint of interest:

- Subjects with missing data at the time point of interest. In the case of ACR50, non-response is imputed if ACR50 cannot be derived (ie: derived as “missing”) based on available ACR components ([Section 8.1.1](#))
- Subjects who remained in the study at the timepoint of interest but discontinuing study treatment before the timepoint of interest (data after IE)
- Subjects with missing Baseline value (for composite or non-composite binary variables based on change(s) from Baseline of continuous endpoint(s)).

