4.2.2.5 Treatment Policy Strategy

Another supportive analysis will be performed on the primary efficacy endpoint to address IE.

The treatment policy strategy will include all available data observed at the week of interest (Week 16) regardless of the occurrence of IE. This means the analysis includes on- and off-treatment values collected after subjects prematurely discontinued study treatment but agreed to remain on the study and continued to attend visits and provide assessments at those visits. Those observed values will be analyzed according to the subject's randomized treatment. Subjects for whom efficacy data cannot be obtained at the week of interest, despite attempts to retain them in the study, will have their data imputed using MI-MCMC / monotone regression ([Section 4.2.2.2](#)) based on non missing data collected up to Week 16.

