8.1.4.7 Tipping point analysis

The degree of the departure from the MAR assumption to overturn conclusions from the primary analysis will be investigated in a tipping point analysis. This analysis will be performed on the monotone missing data and only if the primary analysis is significant at $\alpha=0.05$. Intermittent missing data will be imputed using the MCMC method. In this analysis, it will be assumed that subjects who have missing data and are randomized to BKZ have a lower probability of response compared to subjects who have missing data and are randomized to placebo.

The analysis will be primarily conducted on the binary response endpoint itself in considering the worst-case scenario that subjects who have missing ACR50 response will be set as non-responders if they are randomized to BKZ and as responders if they are randomized to Placebo. If the result tips, then the tipping point analysis will be reconducted on the ACR50 endpoint after having delta-adjusted each individual component of the ACR50 endpoint. For both analyses, the same model as used for the primary efficacy analysis will be conducted on the RS. If the delta parameter value for which the study conclusion under MAR is reversed is plausible, the conclusion under MAR will then be questionable. Refer to [Section 4.2.2.4](#) for more details on the methodology.

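### The worst-case step of the ACR50 tipping-point analysis leaves out placebo subjects observed after discontinuation, so it is not the most adverse case and can wrongly end the tipping-point analysis

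*SAP*

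**What the plan says.** Section 4.2.2.4 sets the rule for both arms in one sentence. On the BKZ side it covers a missing Week 16 ACR50 and adds "or non-missing ACR50 after study treatment discontinuation) will be imputed as non-responders". On the placebo side, "all placebo-randomized subjects with a missing ACR50 at Week 16 will be imputed as responders". The SAP concedes that there is little justification for the scenario but states that "it makes the most putative assumption possible against a BKZ treatment effect".

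The result decides what follows: "If the p-value for the OR of BKZ versus placebo is < 0.05 , then no further tipping point analyses are needed". Otherwise the ACR components are delta-adjusted in each treatment group, and for that step the same section defines the data at issue differently: "where missing values include observations after the IE date and any other missing values".

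Section 8.1.4.7 describes the worst case a second time: "subjects who have missing ACR50 response will be set as non-responders if they are randomized to BKZ and as responders if they are randomized to" the control arm. Here the extension to post-discontinuation values is absent for both arms.

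Two other sections bear on the point. Under non-responder imputation (4.2.2.1), non-responders include "Subjects who remained in the study at the timepoint of interest but discontinuing study treatment before the timepoint of interest (data after IE"). Section 4.2.2.5 plans for Week 16 data of this kind, namely "values collected after subjects prematurely discontinued study treatment but agreed to remain on the study".

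**The concern.** Because the extension is spelled out for BKZ and left out for placebo in the same sentence, missing cannot be read there as silently including post-discontinuation values. A placebo subject who stopped treatment but attended Week 16 is not set to response. The SAP does not say whether that subject keeps the observed value or the non-response assigned in the primary analysis.

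The primary analysis already counts missing and post-discontinuation BKZ subjects as non-responders, so the BKZ half of the step changes nothing. All of the added adversity comes from the placebo half, which is the half that is incomplete.

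A screening step of this kind is valid only if it is at least as adverse as what it screens out. Here it may not be. The delta step treats post-event observations as missing, shifts placebo components toward improvement by growing amounts, and (Step 6) holds BKZ subjects with missing data at non-response. At large shifts it can be more adverse than the step that decides whether it is run. At stake is whether the delta-adjusted analysis of ACR50 is run when it should be.

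**Working it through.** **Design figures.** The SAP states no figure for the worst-case step, so the design figures in section 2.4.1 were reproduced first: 420 BKZ and 280 placebo subjects, 43.8% versus 16%.

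- Difference: 43.8 − 16 = 27.8 points.
- Odds ratio: (0.438/0.562)/(0.16/0.84) = 4.09.
- Power: the continuity correction n′ = (n/4)·[1 + √(1 + 2(1 + 1/k)/(n·d))]², with k = 420/280 = 1.5 and d = 0.278, gives n′ = 280 at n = 274. Power is above 99.99% with or without it, which agrees with the stated >99%.

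**Method.** Unadjusted Wald test of the log odds ratio on expected counts, two-sided at 0.05. Region and bone erosion were not modelled.

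- log OR = ln[a/(420 − a)] − ln[c/(280 − c)]
- SE = √[1/a + 1/(420 − a) + 1/c + 1/(280 − c)]

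Starting counts: BKZ a = 0.438 × 420 ≈ 184; placebo c = 0.16 × 280 ≈ 45. Let m be placebo subjects with missing ACR50 and d placebo subjects observed off treatment, all non-responders at the start. As written, placebo responders become 45 + m; in the full worst case, 45 + m + d. BKZ does not change.

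**Tipping count at the design rates.** Adding 56 placebo responders gives 101/280: OR 1.38, p = 0.041. Adding 57 gives 102/280: log OR = ln(184/236) − ln(102/178) = 0.308, SE = 0.158, OR 1.36, p = 0.052. So 57 of 280 (20.4%) must be missing or off treatment.

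**Assumed splits** (the SAP gives no discontinuation or missingness counts):

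| BKZ vs placebo | m + d | As written | Full worst case |
|---|---|---|---|
| 43.8% vs 16% | 14 + 14 | OR 2.92, p<0.0001 | OR 2.21, p<0.0001 |
| 43.8% vs 16% | 28 + 28 | OR 2.21, p<0.0001 | OR 1.38, p = 0.041 |
| 43.8% vs 16% | 40 + 20 | OR 1.79, p = 0.0004 | OR 1.30, p = 0.097 |
| 43.8% vs 16% | 50 + 7 | OR 1.52, p = 0.009 | OR 1.36, p = 0.052 |
| 30% vs 16% | 10 + 10 | OR 1.75, p = 0.002 | OR 1.42, p = 0.049 |
| 30% vs 16% | 14 + 7 | OR 1.61, p = 0.009 | OR 1.39, p = 0.062 |
| 30% vs 16% | 14 + 14 | OR 1.61, p = 0.009 | OR 1.22, p = 0.26 |

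For the last row a = 0.30 × 420 = 126. As written: ln(126/294) − ln(59/221) = 0.473, SE = 0.181, z = 2.61. Full: ln(126/294) − ln(73/207) = 0.195, SE = 0.173, z = 1.13. At 30% versus 16% the tipping count is 21 placebo subjects (7.5%).

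**Who is affected.** Section 3.4 dates discontinuation at treatment end plus 31 days. If treatment end is the last injection (an assumption), a last injection at Week 12 (Day 85) gives Day 116, after the Week 16 visit at about Day 113; one at Week 10 (Day 71) gives Day 102. Only placebo subjects last injected at Week 10 or earlier who still attended Week 16 would be affected.

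**The case against.** The strongest defence is the composite estimand. Section 8.1.2 defines success as achieving ACR50 without stopping treatment through Week 16, so a placebo subject seen off treatment is a known failure and not a missing value. This does not hold up, because the SAP does not apply that logic in this step: a placebo subject who discontinued and then has no Week 16 value becomes a responder. Turning discontinued placebo subjects into responders only if they missed the visit has no stated reason, and the delta step does not make the distinction.

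A second defence is that this is a drafting slip, since section 8.1.4.7 is worded the same way for both arms. That is plausible, but 8.1.4.7 drops the extension for both arms and does not supply it for placebo. A programmer following 4.2.2.4 would implement the asymmetric rule.

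The objections on size stand. The discontinuation splits have no source in the SAP, the 31-day rule shrinks the affected group, and at the design effect with modest discontinuation the conclusion is the same either way. If no placebo subject has an off-treatment Week 16 value, nothing changes. If such subjects keep observed values and some are already responders, the gap is smaller than calculated.

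A reader might also infer that passing the step switches off all sensitivity analysis, or the only analysis that departs from missing at random. The document does not support that. The per-protocol, modified composite, treatment policy, observed-case and COVID-19 analyses in section 8.1.4 still run, as does the FAS analysis if that set differs from the Randomized Set. Reference-based imputation of the ACR components (4.2.1.3, 8.1.4.4) is itself not a missing-at-random analysis, although it addresses the components and not ACR50. The treatment policy analysis uses the actual values of the subjects in question.

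**Conclusion.** The point holds as an error in the rule. The worst-case step is not the most adverse assumption possible, and it is inconsistent with the delta step it gates and with its second description in 8.1.4.7. The consequence is limited to whether the delta-adjusted tipping-point analysis of ACR50 is run; the primary test and the testing hierarchy are untouched.

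The effect is probably small. At the design rates the full worst case tips only if at least 57 of 280 placebo subjects (20%) are missing or off treatment, and the as-written step then differs only if enough of them were observed off treatment. With an observed effect about half that planned (14 points against 27.8), 21 such subjects are enough, and the two versions can disagree clearly (p = 0.009 against 0.26 with 14 + 14). These figures rest on an unadjusted test, assumed splits, and off-treatment placebo subjects starting as non-responders.

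**What to change.** In section 4.2.2.4, give the placebo clause the same extension as the BKZ clause, so that a placebo subject whose Week 16 ACR50 was observed after treatment discontinuation is also imputed as a responder. In section 8.1.4.7, state the same definition of missing for both arms, matching the one used for the delta step.

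The change costs one phrase in each section. The worst-case p-value may become slightly less favourable, and the delta-adjusted analysis may then have to be run where it would otherwise have been skipped.

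### The Table 4-3 footnote on hs-CRP shifts observed as well as imputed values in the tipping point analysis, contradicting Step 3 and able to change ACR50 in fully observed subjects

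*SAP*

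**What the plan says.** SAP Section 4.2.2.4 sets out the tipping point analysis of the primary endpoint, ACR50 at Week 16. Its delta adjustments are made to each ACR component before ACR50 is derived.

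Most of the section limits the shift to data that were not observed on treatment:

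- The introduction defines the target as missing data, "where missing values include observations after the IE date and any other missing values".
- Step 3: "Imputed values will be shifted using a delta adjustment independently in each treatment group".
- The text below Step 3: "the same delta adjustment value will be applied on the imputed values for the Week 16 visit only".
- Direction on bimekizumab: "A positive shift is applied to the imputed value for subjects randomized to BKZ to increase the imputed value".
- Direction on placebo: "A negative shift is applied to the imputed value for subjects randomized to placebo to decrease the imputed value".
- Step 9: "missing values are adjusted with a larger shift than at the previous iteration".

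The first footnote to Table 4-3 also refers only to the shifted imputed value, and Section 8.1.4.7 restricts the analysis to monotone missing data.

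The second footnote, which concerns hs-CRP alone, differs. It applies the delta adjustment on the natural log scale to "imputed and observed values which will then be exponentiated prior to deriving endpoint".

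**The concern.** A tipping point analysis asks how unfavourable the unobserved outcomes must be before the conclusion is lost. Observed on-treatment data are meant to stay fixed. The hs-CRP footnote breaks that rule for one of the seven ACR components, and it is the only hs-CRP-specific instruction a programmer has.

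If it is followed as written, observed bimekizumab responders can become non-responders and observed placebo non-responders can become responders. The tipping point would come earlier for a reason unrelated to missingness, and the reported delta would no longer describe an assumption about missing data. It would also sit badly with Section 8.1.1, under which a response that can be calculated from observed data is not altered even by imputed values.

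**Working it through.** **1. The plan's own deltas.** Table 4-3 uses 5% of each range: 0.05 × 66 = 3.3 (SJC), 0.05 × 68 = 3.4 (TJC), 0.05 × 3 = 0.15 (HAQ-DI), 0.05 × 100 = 5 (the three VAS components). All reproduce. For hs-CRP the plan gives 5% of the observed log range at Week 16, without a number.

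**2. Size of the hs-CRP delta.** The floor is half the LLOQ of 0.10 mg/L (Section 8.1.1.4), so 0.05 mg/L. The maximum is not in the SAP; 20 to 200 mg/L is assumed here. Then δ = 0.05 × ln(max / 0.05).

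**3. Effect on an observed value.** A log shift of mδ multiplies Week 16 hs-CRP by f = exp(mδ) on bimekizumab and by 1/f on placebo. Baseline is not shifted, so nothing cancels. The true improvement needed to register 50% is 1 − 0.5/f on bimekizumab and 1 − 0.5f on placebo.

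| Assumed max (mg/L) | δ | f at 1δ | Needed at 1δ, BKZ / placebo | Needed at 3δ, BKZ / placebo |
|---|---|---|---|---|
| 20 | 0.300 | 1.35 | 62.9% / 32.5% | 79.6% / −22.8% |
| 50 | 0.345 | 1.41 | 64.6% / 29.4% | 82.3% / −40.9% |
| 100 | 0.380 | 1.46 | 65.8% / 26.9% | 84.0% / −56.4% |
| 200 | 0.415 | 1.51 | 67.0% / 24.3% | 85.6% / −73.5% |

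A negative entry means that a placebo subject whose hs-CRP rose by up to that percentage would still count as 50% improved. Step 9 provides for multiples of delta, so 3δ is within the plan.

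**4. From hs-CRP to ACR50.** hs-CRP is one of five measures of which three must improve, after both joint counts have improved by 50%. Only subjects for whom hs-CRP decides the third measure can change status. An illustrative simulation with no missing data used ACR50 rates near the planning values (43.8% and 16%), a maximum of 100 mg/L, and assumed correlations and SDs:

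| Shift | BKZ responders lost | Placebo responders gained |
|---|---|---|
| 1δ | 0.9% | 0.6% |
| 3δ | 2.1% | 1.7% |

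With the planned 420 and 280 subjects, that is about 4 and 2 subjects at 1δ (0.0086 × 420 = 3.6; 0.0065 × 280 = 1.8) and about 9 and 5 at 3δ (0.0206 × 420 = 8.7; 0.0170 × 280 = 4.8). If only imputed values are shifted, the number is zero at every delta.

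**5. Interaction with the other steps.** Step 6 sets bimekizumab subjects with missing data to non-response after the shift, so the delta cannot alter their final status. Under the literal footnote, the bimekizumab hs-CRP delta would therefore act only through subjects with observed data, whom Step 6 does not protect. The preliminary worst-case analysis (missing on bimekizumab as non-response, missing on placebo as response) is presented as the most extreme assumption against the drug. A delta analysis limited to missing data stays inside that bound; one that shifts observed hs-CRP need not.

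**The case against.** The best defence is that this is a slip of wording. Every other statement confines the shift to imputed or missing values. The footnote may only have meant that the whole hs-CRP column, observed and imputed, is logged and back-transformed, with Step 3 governing which values move. No direction of shift is stated for observed values, since both directional bullets speak of imputed ones. This is probably what was intended, but the footnote's subject is the delta adjustment itself and the text does not say otherwise. Nor can the word observed be read as data after treatment discontinuation, because the section already classes those as missing.

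Three further points limit the importance and stand:

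- **The step may never run.** It needs a significant primary result and a worst-case analysis with p > 0.05. Take 184/420 bimekizumab responders (43.8%) and an unadjusted Wald test of the log odds ratio. With 101/280 placebo responders, z = 0.323/0.159 = 2.04; with 102/280, z = 0.308/0.158 = 1.94. The worst case therefore first fails at 102 placebo responders, about 57 more than the planned 16% (44.8). Roughly 20% of the placebo arm (57/280) would have to be missing at Week 16.
- **Few subjects would change status**, as the simulation shows.
- **The distortion runs against bimekizumab.** It could make the result look more fragile than it is, but not falsely robust.

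**Conclusion.** The concern holds. The hs-CRP footnote contradicts Step 3 and the rest of the tipping point text, nothing in the SAP reconciles them, and followed literally it changes ACR50 for some fully observed subjects.

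Its importance is low. It touches a contingent supportive analysis and leaves the primary test, the testing hierarchy and the type I error untouched. The hs-CRP threshold figures rest on an assumed maximum, and the ACR50 figures also rest on assumed correlations and SDs. The contradiction itself rests on neither.

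**What to change.** Reword the second footnote to Table 4-3 along these lines: imputed Week 16 hs-CRP values, including those replacing observations after treatment discontinuation, are log-transformed, shifted by delta and exponentiated before ACR50 is derived; observed on-treatment hs-CRP values are not shifted.

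The cost is one sentence in the SAP and a check that the hs-CRP program follows it. No other analysis changes.

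### Step 6 of the tipping-point analysis cancels the BKZ shift, leaving a placebo-only sweep that cannot give a tipping point for each arm or the departure from MAR that section 8.1.4.7 judges

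*SAP*

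**What the plan says.** Section 4.2.2.4 of the SAP begins with a worst case: missing BKZ subjects become non-responders and missing placebo subjects become responders. If that gives p > 0.05, delta adjustments follow, made "in each treatment group independently with various degrees of plausibility with the goal to find for each treatment group the" tipping point.

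The steps that matter here are:

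- **Step 3.** For components where a high score is unfavourable, "A positive shift is applied to the imputed value for subjects randomized to BKZ to increase the imputed value", and "A negative shift is applied to the imputed value for subjects randomized to placebo to decrease the imputed value". Table 4-3 sets the initial delta at 5% of each component's range.
- **Step 6.** BKZ subjects with missing data, including observations after the intercurrent event, "should be set to non-response, after applying the delta adjustment outlined in Step 3 above". The reason given is: "This ensures subjects randomized to BKZ do not have a higher probability of response in the tipping point analyses compared to the primary analysis". Placebo subjects are not reset.
- **Step 9.** Steps 3 to 8 are repeated with larger shifts until the p-value is no longer significant.

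Section 8.1.4.7 states the aim: "The degree of the departure from the MAR assumption to overturn conclusions from the primary analysis will be investigated in a tipping point analysis". Its decision rule is: "If the delta parameter value for which the study conclusion under MAR is reversed is plausible, the conclusion under MAR will then be questionable".

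The primary analysis in section 8.1.2 imputes non-response in both arms (NRI). It is not a MAR analysis.

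**The concern.** A shift that is applied to imputed values and then overwritten does nothing. The plan promises a tipping point for each arm, but only the placebo delta can move the p-value. How poorly BKZ dropouts would have to do before the conclusion changed is never explored.

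The rule in section 8.1.4.7 is affected too. It asks whether the tipping delta is a plausible departure from MAR. Under Step 6 the BKZ arm is never under MAR at any point of the sweep. The delta reported is the placebo shift needed once BKZ is already at its floor, which is a different quantity from a departure from MAR in both arms. A reader of the table would probably take it for the latter.

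**Working it through.** **1. The plan's own figures.** These reproduce.

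- Odds ratio: (0.438/0.562)/(0.16/0.84) = 4.09, as in section 2.4.1.
- Power with 420 and 280 subjects: above 99%, with or without continuity correction.
- Table 4-3 deltas: 0.05 × 66 = 3.3; 0.05 × 68 = 3.4; 0.05 × 3 = 0.15; 0.05 × 100 = 5.

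**2. Why the BKZ delta drops out.** Let a and b be the responders with observed data in the BKZ and placebo arms. Let x_B and x_P be the responders among the imputed subjects in imputation i. Without covariates, the log odds ratio is

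ln[(a + x_B)/(420 − a − x_B)] − ln[(b + x_P)/(280 − b − x_P)].

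Step 3 makes x_B depend on the BKZ delta and x_P on the placebo delta. Step 6 then sets x_B = 0 in every imputation. The estimate, its variance and the Rubin-combined p-value contain no BKZ delta. Adding region and bone erosion changes nothing, because the outcomes entering the model are the same for every BKZ delta.

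**3. Numerical illustration.** Steps 1 to 9 were simulated with 420 and 280 subjects, seven components, Table 4-3 steps and 100 imputations combined by Rubin's rules. Assumptions not in the SAP: 25% missing per arm, the component distributions, an hs-CRP log range of 8, same-arm hot-deck draws in place of MCMC and regression, and an unadjusted Wald test. The simulated NRI rates were 21.4% vs 5.4% (run A) and 15.2% vs 8.2% (run B), not the planned rates. The table gives p-values by BKZ delta, in multiples of the Table 4-3 step.

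| Run, placebo delta | Step 6 | ×0 | ×1 | ×2 | ×4 | ×10 |
|---|---|---|---|---|---|---|
| A, ×2 | without | <0.0001 | 0.002 | 0.007 | 0.008 | 0.008 |
| A, ×2 | with | 0.008 | 0.008 | 0.008 | 0.008 | 0.008 |
| A, ×4 | without | 0.010 | 0.188 | 0.382 | 0.416 | 0.416 |
| A, ×4 | with | 0.416 | 0.416 | 0.416 | 0.416 | 0.416 |
| B, ×0 | without | 0.003 | 0.032 | 0.102 | 0.131 | 0.131 |
| B, ×0 | with | 0.131 | 0.131 | 0.131 | 0.131 | 0.131 |

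- With Step 6 every row is constant in the BKZ delta.
- A placebo tipping point is still found: in run A, between ×2 (p = 0.008) and ×4 (p = 0.416).
- Without Step 6 a BKZ tipping point exists: in run B at placebo ×0, between ×1 and ×2.
- When both arms move by the same multiple, the significance decision is the same with and without Step 6 at ×1, ×2 and ×4 in run A (for example 0.007 and 0.008 at ×2). In run B the result has already tipped at ×1 either way (0.167 and 0.457).

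In both runs the worst-case result is significant in favour of placebo, so a literal two-sided reading of the p < 0.05 gate would have stopped before the delta steps. The grids show only how p depends on the deltas.

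**4. When the delta steps run.** Unadjusted Wald test on the worst case:

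- Planned rates taken as NRI rates: 184/420 vs (45 + 57)/280. The log odds ratio is 0.308, SE 0.158, p = 0.052. So about 57 of 280 placebo subjects (20%) must be missing.
- Planned rates taken as full-data rates, with equal missingness m: BKZ 420 × 0.438 × (1 − m) responders, placebo 280 × [0.16 × (1 − m) + m]. This gives p = 0.044 at 16% and 0.097 at 17%.

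**The case against.** Step 6 is deliberate and explained. The primary analysis is NRI, and section 4.2.2.4 aims at assumptions that overturn the main analysis. Relative to that anchor BKZ is already at its floor, and lifting the reset would let missing BKZ subjects count as responders, which the primary analysis does not allow. This stands. It justifies the reset and makes simply removing Step 6 contestable. It does not justify keeping a BKZ shift, a per-arm goal and MAR wording that the reset empties.

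The analysis is also supportive, lies outside the testing hierarchy, errs against BKZ and is reached only with heavy missingness. That stands too and limits the weight of the point.

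Some stronger readings are tempting but not supported:

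- **That nothing is measured.** Placebo values start from MAR-based imputation and are shifted further at each iteration, so a placebo tipping point given BKZ non-response is obtained.
- **That the sweep starts from a mislabelled delta-zero row.** The SAP starts at 5% of range and only enlarges it.
- **That the primary result would be called questionable.** Section 8.1.4.7 says this of the conclusion under MAR.
- **That tipping comes at a materially smaller delta.** The equal-step comparison above does not show it. A calculation on one latent component at the planned rates does change the decision in some cases (30% missing, one latent SD in each arm: p = 0.21 with Step 6, 0.024 without), but that scale cannot be mapped to Table 4-3.

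One textual exception cuts the other way. Footnote 2 of Table 4-3 puts the hs-CRP delta on observed as well as imputed values. Read literally, a BKZ delta could then reach subjects whom Step 6 does not reset. Step 3 and footnote 1 limit the shift to imputed values, so this looks like a slip.

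**Conclusion.** The contradiction is in the text and needs no assumption: with Step 6 in force, the BKZ delta on imputed values has no effect. The procedure is a one-dimensional placebo sweep with BKZ fixed at non-response. It cannot deliver the BKZ half of the stated goal, and its tipping delta is not the quantity that the plausibility rule in section 8.1.4.7 describes.

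The practical size is modest. The primary analysis is untouched and any bias is conservative for BKZ. The delta steps run only with about 16 to 20% missing or more at the planned rates; the SAP gives no expected missingness, and a smaller observed effect would lower that threshold. The simulated p-values depend on the assumptions listed and show the pattern only.

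**What to change.** 1. Keep the Step 6 sweep, delete the BKZ shift from it, and label it as the placebo tipping point given that missing BKZ subjects are non-responders.
2. Beside it, report a two-way grid of odds ratios and p-values over the BKZ and placebo deltas, without Step 6, starting at (0, 0), where imputation is MAR within each arm. Apply the plausibility rule of section 8.1.4.7 to this grid only.
3. If the grid is not added, delete the per-arm goal in section 4.2.2.4 and the MAR wording in section 8.1.4.7.
4. Correct footnote 2 of Table 4-3 so that the hs-CRP delta applies to imputed values only. Also correct Step 8, which cites Step 6 for the logistic regressions that Step 7 now describes.

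The cost is SAP wording and a few extra runs of an existing program. No new data are needed, and the primary analysis does not change.
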